### 9.2.2 Relationship to Study Drug

The Investigator's assessment of an AE's relationship to study treatment is part of the documentation process, but it is not a factor in determining what is or is not reported in the study.

The relationship or association of the study drug in causing or contributing to the AE will be characterized using the following classification and criteria presented in [Table 7](#).

**Table 7 Guidelines for Determining the Relationship (if any) Between Adverse Event and the Study Drug**

AE Relationship	Definition
Definite	This relationship suggests that a definite causal relationship exists between treatment administration and the AE, and that other conditions (concurrent illness, progression/expression of disease state, or concurrent medication reaction) do not appear to explain the event. The event reappears or worsens if the study treatment is re-administered.
Probable	This relationship suggests that a reasonable temporal sequence of the event with treatment administration exists and, based upon the known pharmacological action of the treatment, known or previously reported adverse reactions to the treatment or class of treatment, or judgment based on the Investigator’s clinical experience, the association of the event with the study treatment seems likely. The event disappears or decreases on cessation of study treatment.
Possible	This relationship suggests that the study treatment caused or contributed to the AE, ie, the event follows a reasonable temporal sequence from the time of treatment administration or follows a known response pattern to the study treatment, but could also have been produced by other factors.
Unlikely Related	This relationship suggests an improbable (but not impossible) association between the study medication and the reported event.
Not Related	This relationship suggests no association between the study treatment and the reported event.

Abbreviations: AE = adverse event.

### 9.3 SERIOUS ADVERSE EVENTS

#### 9.3.1 Serious Adverse Event Criteria

An SAE is defined as any event that results in death, is immediately life threatening, requires inpatient hospitalization or prolongation of existing hospitalization, results in persistent or significant disability/incapacity, or is a congenital anomaly/birth defect not present at Prescreening. Important medical events that may not result in death, be life threatening, or require hospitalization may be considered SAEs when, based upon appropriate medical judgment, they may jeopardize the patient or may require medical or surgical intervention to prevent one of the outcomes listed in this definition. Examples of such medical events include allergic bronchospasm requiring intensive treatment in an emergency room or at home, blood dyscrasias or convulsions that do not result in inpatient hospitalization, or the development of drug dependency or drug abuse.

Serious AEs must be reported ([Section 9.3.3](#)) and will be followed through resolution. Serious AEs that occur after the final follow-up visit need not be reported unless the Investigator considers them related to study drug.

#### 9.3.2 Serious Adverse Event Follow-up

Appropriate remedial measures should be taken by the Investigator using his/her best medical judgment to treat the SAE. These measures and the patient’s response to these measures should be recorded. All SAEs regardless of relationship to study drug will be followed by the

[REDACTED]

[REDACTED]

[REDACTED]

[REDACTED]

[REDACTED]

[REDACTED]

[REDACTED]

[REDACTED]

[REDACTED]

[REDACTED]

[REDACTED]

[REDACTED]

[REDACTED]

## 9.4 OVERDOSE

The study drugs are planned to be administered by trained study staff. Administration will be performed in accordance with the IB and instructions in the Pharmacy Manual. Any incidence of overdose should be recorded as an SAE.

No clinical data are available regarding overdose with WVE-120101. As with any agent, if overdose occurs, general supportive measures and close observation should be instituted. Misuse of the study drug for illegal purposes is not expected in this study as patients have no direct access to the study drugs.

## 9.5 PREGNANCIES

If a female subject becomes pregnant during the study, she must be discontinued from study drug but the patient may continue to be followed in the study. The Medical Monitor should be notified by the Investigator and a Pregnancy Notification Form should be completed. The patient should be followed until the outcome of the pregnancy is known.

Pregnancy in and of itself is not an SAE. However, complications of the pregnancy should be reported to the sponsor within 24 hours of knowledge by the Investigator (eg, if the mother is hospitalized for dehydration) and an SAE form must be completed.

## 10 STATISTICAL METHODS

### 10.1 GENERAL CONSIDERATIONS

Statistical analysis will be performed using SAS software Version 9.4 or later. Continuous variables will be summarized using the mean, standard deviation (SD), median, minimum value, and maximum value. Categorical variables will be summarized using frequency counts and percentages. Patient-level data will be presented in data listings.

Analyses will primarily be descriptive; confidence intervals will be presented where appropriate.

Details on the statistical analysis will be provided in the Statistical Analysis Plan (SAP).

### 10.2 SAMPLE SIZE DETERMINATION

The sample size was not calculated on the basis of statistical hypothesis testing. However, based on the results of Wild et al., for each of the active doses, 9 patients per active dose group will yield a two-sided 90% confidence interval width for mHTT in CSF of approximately  $\pm 110$  fM.

## 10.3 STUDY PATIENTS

### 10.3.1 Analysis Populations

The following study populations will be evaluated:

- Safety population will include all randomly assigned patients who receive at least 1 dose of WVE-120101.
- PD population will include all patients in the safety population who have at least 1 postbaseline CSF sample.
- PK population will include all patients in the safety population who have sufficient plasma or CSF concentration data, as determined by the pharmacokineticist, for inclusion in the descriptive statistical analysis.
- Per Protocol Population will include all patients in the Safety population who have no major protocol deviations.

The Safety population will be used for the safety analysis, demographics, and other baseline patient characteristics; the PD population will be used for the PD analysis; the PK population will be used for the PK analysis; and the Per Protocol population will be used for all analyses of clinical effects.

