## **3.2 STUDY ENDPOINTS**

### **Primary Endpoint**

The primary endpoint is the safety and tolerability of WVE-120101, as compared with placebo, as assessed by the number of patients with adverse events (AEs), severity of AEs, number of patients with serious AEs (SAEs), and the number of patients who withdraw due to AEs.

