#### **Clinical Effects**

- Change from baseline (baseline value to the last measured time point) and difference from placebo in the TFC, administered as part of the UHDRS.

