### **6.2.1.2 Placebo**

Placebo will be 0.9% Sodium Chloride Injection sterile, preservative-free solution administered alone via the IT route. It will be provided in commercially available single-use vials or plastic ampoules. Placebo, as prepared by an unblinded study pharmacist in a dosing solution for injection, will be visually identical in appearance to the WVE-120101 injection solution.

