### **6.2.2 Administration of Study Drug and Collection of CSF**

Study drug (WVE-120101 or placebo) will be administered as a single dose followed by multiple doses (3 doses at 4-week intervals). The route of administration will be IT by direct lumbar injection, and the total volume of the injection will be 10 mL. The lumbar puncture will be performed by an appropriately trained individual. Within 1 week prior to the lumbar puncture, a blood sample will be tested locally for platelet count and prothrombin time to confirm that it is safe to proceed with the lumbar puncture ([Section 8.2.6](#)). Patients should not be sedated during administration of study drug. Detailed instructions on the procedure to be used for lumbar puncture are provided in the Study Operations Manual.

Within  $\leq 15$  minutes prior to administration of study drug, CSF samples will be collected for safety assessments ([Section 8.2.7](#)), exposure ([Section 8.3](#)), and PD ([Section 8.4](#)), per the Schedule of Assessments ([Table 1](#), [Table 2](#), and [Table 3](#)). Additional CSF collected will be stored and used for research purposes. No more than 10 mL of CSF total should be collected.

Immediately after each administration of study drug, all patients should be ambulatory and active for approximately 30 minutes postdose. The Investigator should note any subtle weakness or fatigue during this period. In addition, formal physical examinations targeting the neurological system, will be performed at the time points noted in the Schedule of Assessments ([Table 1](#), [Table 2](#), and [Table 3](#)). Any postdose SAEs will be monitored until resolution.

Cerebrospinal fluid samples will only be used by the Sponsor and/or a contracted vendor for research related to the development of treatments for HD and will be stored for a maximum of 10 years. All biological material will be stored and secured in a way that ensures that unauthorized access is prohibited and the samples are not lost, deteriorated, or destroyed accidentally or illegally. Detailed instructions for sample collection, storage, processing, and shipping will be provided in the Laboratory Manual.

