### **10.3.5 Prior and Concomitant Medications**

Prior and concomitant medications will be summarized separately by the number and percentage of patients per dose cohort for each World Health Organization (WHO) drug class and PT. Medications will be coded using the WHO drug dictionary, Anatomical Therapeutic Chemical (ATC) classes, and PT. Patients will be counted only once for a given prior or concomitant medication.

Medications with a start date before the first dose of study drug will be classified as prior medications. Any medication that the patient began taking after the first dose of study drug will be classified as concomitant. Any medication that a patient started before the first dose of study drug and continued to take during the study will be classified as both prior and concomitant. Any medication that was stopped on the same day as the first dose of study drug will be considered a prior medication. If the stop date of a given medication is missing, then the medication will be classified as concomitant.

Concomitant and prior medications will be presented by patient in data listings.

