### **10.3.6 Study Drug Exposure and Compliance**

Exposure to study drug, duration of exposure, and overall treatment compliance will be summarized. Study drug dosing information will be presented by patient in data listings.

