## **10.9 SAFETY ANALYSES**

Safety data will be analyzed descriptively overall and by treatment group and dose cohort, and no formal statistical comparisons will be performed. Data from unscheduled visits (laboratory tests, vital signs, physical examinations, and ECGs) will not be included in the tables, but will be included in the by-patient listings.

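### The Safety population is defined by receipt of WVE-120101, so as written no placebo patient belongs to any analysis population

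*Combined protocol and SAP*

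**What the plan says.** Section 10.3.1 defines the population for the primary analysis: "Safety population will include all randomly assigned patients who receive at least 1 dose of WVE-120101". The PD, PK and Per Protocol populations are then each built from patients already in Safety. The same section assigns Safety to the safety, demographic and baseline tables, PD to the PD analysis, and Per Protocol to all clinical effects.

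Other sections require a placebo comparison. Section 3.2 says "The primary endpoint is the safety and tolerability of WVE-120101, as compared with placebo", and the secondary clinical endpoint is the change from baseline and "difference from placebo in the TFC, administered as part of the UHDRS". Section 10.9 says "Safety data will be analyzed descriptively overall and by treatment group and dose cohort".

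On what placebo is, Section 6.2.1.2 says "Placebo will be 0.9% Sodium Chloride Injection sterile, preservative-free solution administered alone via the IT route". Section 6.2.2 supplies a term that covers both arms: "Study drug (WVE-120101 or placebo) will be administered as a single dose followed by multiple doses".

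**The concern.** A placebo patient receives no WVE-120101 and so cannot meet the Safety definition. Because the other three populations are nested in Safety, that patient cannot meet any of them.

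Followed literally, the tables for the primary endpoint would have no placebo column, and the difference from placebo in TFC could not be computed. Baseline characteristics and CSF mHTT would also be shown for active patients only. Section 2.1 justifies the placebo group as the reference for safety and as the means of separating drug effects from those of lumbar puncture and intrathecal injection. In a descriptive study the side-by-side tables are the result, so losing the placebo column removes that reference from the reported summaries.

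**Working it through.** **Planned numbers.** Section 4.1 gives five dose cohorts. Sections 4.1 and 6.1 give 9 active and 3 placebo patients in each.

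- Total: 5 × (9 + 3) = 60, which reproduces the approximately 60 in Section 5.
- Active: 5 × 9 = 45. Placebo: 5 × 3 = 15. Placebo share: 15/60 = 25%.
- The sentinel scheme agrees: 1 + 8 = 9 active and 1 + 2 = 3 placebo per cohort.

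**Applying the definitions.** Safety requires random assignment and at least one dose of WVE-120101. Placebo is saline alone, so the second condition fails for every placebo patient: 0 of 3 per cohort and 0 of 15 overall. Per cohort, 9 of 12 patients (75%) qualify. The nested populations can contain no more than Safety does.

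| Population | Used for | Planned maximum as written (active / placebo) | If it read study drug (active / placebo) |
|---|---|---|---|
| Safety | Primary endpoint, demographics, baseline | 45 / 0 | 45 / 15 |
| PD | CSF mHTT | 45 / 0 | 45 / 15 |
| Per Protocol | TFC, other UHDRS subtests, PBA-s | 45 / 0 | 45 / 15 |
| PK | Plasma and CSF drug concentrations | 45 / 0 | 45 / 0 expected |

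Placebo patients have no drug concentrations to analyse, so their absence from PK is harmless. The damage is to Safety, PD and Per Protocol.

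**Is the wording deliberate?** Other rules in Section 10 that depend on dosing use the two-arm term. Section 10.3.5 says "Any medication that the patient began taking after the first dose of study drug will be classified as concomitant". Section 10.3.6 says "Exposure to study drug, duration of exposure, and overall treatment compliance will be summarized". The TEAE definition in Section 10.9.1 is likewise anchored to the first dose of study drug. Among these rules, only the population definition names the active product. That points to a slip rather than an intention to exclude placebo.

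**Does another passage bring placebo patients back in?** The multiple-dose text in Section 4.1 speaks of patients receiving three doses of WVE-120101, with no mention of placebo. Taken literally, placebo patients who roll over would then qualify for Safety. That reading does not survive: Section 6.2.2 gives WVE-120101 or placebo for both the single and the multiple doses, and the schedules of assessments label the multiple-dose phase double-blind. Even if it did survive, placebo patients who had only the single dose would remain outside.

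**Where placebo patients still appear.** They are counted in disposition (Section 10.3.2), included in immunogenicity (Section 10.6), shown in the by-patient adverse event listings (Section 10.9.1), and seen unblinded by the Safety Monitoring Committee (Sections 4.3.1 and 4.3.4.1).

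**The case against.** The best defence is that nobody would be misled. The protocol sometimes uses the product name for both arms, as in the multiple-dose text of Section 4.1 and the individual stopping rules of Section 4.3.4.2. It is selective to read those passages in context and Section 10.3.1 literally. The intent is plain from the endpoints and from Section 10.9, and a programmer would notice an empty placebo arm at once. Section 10.1 defers detail to an SAP that was not supplied, so the error cannot be shown to reach any table. Analyses are descriptive, no sample-size figure changes, and the text can be corrected with no data lost.

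Much of this stands. The slip is probable, the intent is clear, and the final tables may well be right. It does not make the definition correct. Population flags are programmed from this sentence, and a term covering both arms was available and used in neighbouring sections. Deferral to an SAP is no answer when the protocol's own sentence is wrong rather than merely incomplete. Reversibility is a reason to correct it promptly, not to leave it.

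**Conclusion.** The concern holds and the definition must be corrected. As written, 0 of the 15 planned placebo patients (25% of 60) belong to any of the four populations. This contradicts the primary endpoint, the TFC endpoint and the safety summaries by treatment group, and it also empties the placebo side of the baseline and PD tables.

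The counts assume the initial planned cohorts. Cohort expansion (Section 4.3.3), replacements (Section 5.3.3) and direct entrants to multiple dosing (Section 6.1) can change the totals, but under the literal wording placebo stays at 0. Confidence is high for what Section 10.3.1 says; what the final tables will show is not known. The harm is confined to summary tables, because placebo data remain collected, listed and monitored. Power and sample size are unaffected.

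**What to change.** In Section 10.3.1, replace WVE-120101 in the Safety definition with study drug (WVE-120101 or placebo), and carry this into the SAP. PD and Per Protocol then include placebo patients by inheritance. That substitution alone removes the error.

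Three clarifications belong in the same edit:

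- State that patients entering the multiple-dose portion directly are included. Section 6.1 gives them the treatment of an earlier patient, and Table 3 has a treatment-assignment row where Tables 1 and 2 have randomization, so it is unclear whether they count as randomly assigned.
- State that safety is analysed by treatment received.
- Limit PK to WVE-120101 recipients.

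Two minor points are separate from this error and can be tidied at the same time. Sections 10.3.3, 10.5 and 10.8.1 specify tables by dose cohort only, although each cohort contains both arms; say that placebo has its own column. Section 10.5 fixes baseline at Day 1, whereas Table 3 sets it at Day 56 (Day 28 at 32 mg) for direct entrants; align the two.

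The cost is one line for the definition and one for each minor point, with no new data, visits or procedures. The one added burden is that analysis by treatment received needs a stated rule for a patient given both treatments in error. Make the change before the sponsor produces any of the unblinded summaries by treatment group allowed in Section 10.10, so that populations are not redefined after results are seen.

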### 10.3.2 Patient Disposition

The number and percentage of patients screened, randomized, and included in the safety, PK, PD, and Per Protocol populations, and those who complete the study will be presented by dose cohort. The number and percentage of randomized patients who withdraw prior to completion and the primary reason for withdrawal will be summarized by dose cohort.

Study completion information, will be presented by patient in a data listing. A by-patient listing of patients who are screen failures, and the reason for screen failure, will also be presented.

### 10.3.3 Demographics and Other Baseline Characteristics

Summary statistics for demographic and other baseline characteristics data will be provided by dose cohort for the safety population.

Medical history will be summarized by dose cohort and overall using system organ class (SOC) and preferred term (PT). Events will be summarized by patient incidence rates; therefore, in any tabulation, a patient contributes only once to the count for a given PT.

Medical history findings including the verbatim term will be presented by patient in a data listing. Demographic and baseline data will be provided by patient in data listings.

### 10.3.4 Protocol Deviations

Assessment of protocol deviations as ‘minor’ or ‘major’ will be determined blinded to treatment and prior to database unblinding. A protocol deviations log will be finalized before unblinding and final database lock. Protocol deviations will be presented by patient in a data listing.

### **10.3.5 Prior and Concomitant Medications**

Prior and concomitant medications will be summarized separately by the number and percentage of patients per dose cohort for each World Health Organization (WHO) drug class and PT. Medications will be coded using the WHO drug dictionary, Anatomical Therapeutic Chemical (ATC) classes, and PT. Patients will be counted only once for a given prior or concomitant medication.

Medications with a start date before the first dose of study drug will be classified as prior medications. Any medication that the patient began taking after the first dose of study drug will be classified as concomitant. Any medication that a patient started before the first dose of study drug and continued to take during the study will be classified as both prior and concomitant. Any medication that was stopped on the same day as the first dose of study drug will be considered a prior medication. If the stop date of a given medication is missing, then the medication will be classified as concomitant.

Concomitant and prior medications will be presented by patient in data listings.

### **10.3.6 Study Drug Exposure and Compliance**

Exposure to study drug, duration of exposure, and overall treatment compliance will be summarized. Study drug dosing information will be presented by patient in data listings.

## **10.4 PHARMACOKINETIC ANALYSES**

The plasma and CSF WVE-120101 concentration data will be summarized for patients in the PK population.

The individual patient plasma concentration-time data will be listed and displayed graphically on linear and log scales. The plasma concentration-time data will be summarized descriptively in tabular and graphical formats (linear and log scales).

For each cohort, the plasma WVE-120101 concentration data will be analyzed by noncompartmental PK analysis. The parameters listed in [Table 8](#) and [Table 9](#) will be determined. Additional PK parameters may be evaluated if deemed appropriate. Pharmacokinetic parameters for each dose cohort will be compared across WVE-120101 dose levels.

The CSF concentration data will be summarized in tabular format.

**Table 8 Pharmacokinetic Parameters of WVE-120101 after Single-Dose Administration**

Parameter	Definition
$C_{max}$	Maximum observed concentration
$t_{max}$	Time of occurrence of $C_{max}$
$AUC_{0-t}$	Area under the plasma concentration-time curve from time zero to the last quantifiable concentration

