  - m On Day 1, sentinel patients will have blood samples for PK analysis collected predose, 30 minutes ( $\pm 5$  minutes), 1, 2, 4 hours ( $\pm 15$  minutes), 12 hours ( $\pm 2$  hours), 24 hours and 48 hours ( $\pm 4$  hours) postdose. All other patients will have blood samples for PK analysis collected predose and 30 minutes ( $\pm 5$  minutes), 1, 2, 4 hours ( $\pm 15$  minutes), 12 hours ( $\pm 2$  hours), and 24 hours ( $\pm 4$  hours) postdose on Day 1. On Day 112, all patients will have blood samples collected for PK analysis predose and 1, 2, and 4 hours ( $\pm 15$  minutes) postdose. On all other dosing days, PK samples will be collected predose only. On non-dosing days noted, PK will be collected once.
  - n Blood sample for assessment of antibodies to WVE-120101 will be obtained predose (within 1 week prior to injection) or on non-dosing days, as indicated.
  - o On dosing days, CSF sample will be collected  $\leq 15$  minutes prior to study drug administration. No more than 10 mL of CSF total should be collected. CSF samples must be tested locally for safety for the following parameters: total protein, glucose and cell counts (white blood cell counts with differential) on all noted visits.
  - p Immediately after study drug administration, patients should be active for approximately 30 minutes postdose.
  - q All patients will remain in the clinic and have AEs and concomitant medications recorded through 24 hours postdose. In addition, 2 sentinel patients will remain in the clinic and have AEs and concomitant medications recorded throughout the 48-hour postdose period.
  - r This lumbar puncture is optional for patients who terminate early.

**Table 2 Schedule of Assessments for Patients Participating in Both the single and Multiple Dose Portions of the Study (32 mg Cohort)**

Visit	Pre-Screening a	Screening b	Double-Blind Treatment (Single Dose)		Sentinel Patient Follow-up	Follow-up	Double-Blind Treatment (Multiple Dose)			Follow-up		
	1	2	3	4	5	6	7 c	8	9	10 or ET	11	12
Week		-4 to 0	0	0	0	2	4	8	12	16	24	26
Study Day (Visit Window, if applicable) Event/Assessment		Day -28 to -1	Day -6 to Day 1 (Baseline)	Day 2 (24 ± 4h postdose)	Day 3 (48 ± 4h postdose)	Day 14 (±2)	Day 28 (±3)	Day 56 (±3)	Day 84 (±3)	Day 112 or ET (±5)	Day 168 (±5)	Day 182(EOS) (±5) d
Pre-dose/Non-dosing Days												
Patient informed consent form (ICF) Signed	X	X										
Inclusion/exclusion criteria		X	X				X					

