- o On dosing days, CSF sample will be collected  $\leq 15$  minutes prior to study drug administration. No more than 10 mL of CSF total should be collected. CSF samples must be tested locally for safety for the following parameters: total protein, glucose and cell counts (white blood cell counts with differential) on all noted visits.
- p Immediately after study drug administration, patients should be active for approximately 30 minutes postdose.
- q All patients will remain in the clinic and have AEs and concomitant medications recorded through 24 hours postdose. In addition, 2 sentinel patients will remain in the clinic and have AEs and concomitant medications recorded throughout the 48-hour postdose period.
- r This lumbar puncture is optional for patients who terminate early.
- s On Day 1, all patients will have urine samples for PK analysis collected at 0 to 4 hours, 4 to 8 hours, and 8 to 24 hours postdose.

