- j Clinical laboratory safety testing, including clinical chemistry, hematology, and urinalysis. Within 1 week prior to lumbar puncture, a blood sample will be tested to confirm platelet count and prothrombin clotting time. Clinical laboratory safety testing will be performed predose on all dosing days. On Day 56 (Day 28 for 32 mg cohort) only, samples for clinical chemistry and hematology measures (CBC, complement, and fibrinogen only) will also be collected at 1 and 4 hours (±15 minutes) postdose. On all non-dosing days, clinical laboratory safety testing will be performed just

- once. On Day 196 (Day 168 for 32 mg cohort), only platelet count and prothrombin clotting time need to be assessed (prior to CSF sample). Urinalysis will be performed predose on all dosing days, and once on all other days noted.
- k Blood samples for the Prescreening assays to determine eligibility.
  - l On Day 56 (Day 28 for 32 mg cohort), all patients will have blood samples collected for PK analysis predose and 30 minutes ( $\pm 5$  minutes), 1, 2, 4 hours ( $\pm 15$  minutes) postdose. On Day 112 (Day 84 for the 32 mg cohort), all patients will have blood samples collected for PK analysis predose and 1, 2, and 4 hours ( $\pm 15$  minutes) postdose. On all other dosing days, PK samples will be collected predose only. On non-dosing days noted, PK will be collected once.
  - m Blood sample for assessment of antibodies to WVE-120101 will be obtained predose (within 1 week prior to injection) or on non-dosing days, as indicated.
  - n On dosing days, CSF sample will be collected  $\leq 15$  minutes prior to study drug administration. No more than 10 mL of CSF total should be collected. CSF samples must be tested locally for safety for the following parameters: total protein, glucose and cell counts (white blood cell counts with differential) on all noted visits.
  - o Immediately after study drug administration, patients should be active for approximately 30 minutes postdose.
  - p This lumbar puncture is optional for patients who terminate early.
  - q Visit, week, and day for the 32 mg cohort.

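### The only single-dose AUC in Table 8 (AUC0-t) has an end time that varies with dose and sampling, so comparing it across dose levels can make dose-proportional kinetics look more than proportional

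*Combined protocol and SAP*

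**What the plan says.** Table 8 gives three single-dose parameters: Cmax ("Maximum observed concentration"), tmax, and AUC0-t ("Area under the plasma concentration-time curve from time zero to the last quantifiable concentration"). It has no area over a fixed interval, no AUC to infinity and no terminal rate constant; Table 9 lists the rate constant for multiple dosing only.

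Section 10.4 states that "the plasma WVE-120101 concentration data will be analyzed by noncompartmental PK analysis" and that "Pharmacokinetic parameters for each dose cohort will be compared across WVE-120101 dose levels". It also says "Additional PK parameters may be evaluated if deemed appropriate", without naming any. It does not give a trapezoid rule, a rule for values below LLOQ, or a statement on which samples enter AUC0-t.

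The plasma samples after the first dose come from the schedules in Section 4.2:

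- Sentinels (1 active patient per cohort): predose, 0.5, 1, 2, 4, 12, 24 and 48 h.
- All other single-dose patients: the same, without 48 h.
- Later samples: Day 14 and Day 28 ("On non-dosing days noted, PK will be collected once"). In the 2 to 16 mg cohorts a Day 56 predose sample also precedes the second dose. In the 32 mg cohort the Day 28 sample is itself the predose sample for dose 2.

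**The concern.** AUC0-t is comparable across doses only if t is the same at each dose. Here t is set by the assay limit. If kinetics are proportional, a 32 mg curve is 16 times a 2 mg curve and crosses LLOQ later, so more of it is counted. The dose-normalised area can then rise with dose although nothing about clearance has changed.

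The sampling grid makes this a step effect. Gaining one more quantifiable sample extends the area from 4 to 12 h, from 12 to 24 h, or from 24 h to Day 14. With dosing on Day 1, Day 14 is 13 × 24 = 312 h after dosing. In a non-sentinel the last step is therefore a single trapezoid over 312 − 24 = 288 h with no sample inside it, and its area depends heavily on a rule that Section 10.4 does not state.

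Plasma PK is a secondary objective. A rising area per mg could be read as saturating clearance at the top doses when it reflects only where the curves were cut.

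**Working it through.** The plan gives no numeric value for AUC0-t, so there is no figure to reproduce. The check takes exactly proportional curves, samples them at the protocol times, cuts each at its last value at or above LLOQ, and compares AUC0-t per mg at 32 mg with 2 mg. The true ratio is 1.00.

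**Inputs from the protocol:** doses of 2, 4, 8, 16 and 32 mg; samples at 0, 0.5, 1, 2, 4, 12 and 24 h, then Day 14 (312 h) and Day 28 (27 × 24 = 648 h).

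**Assumed, because the documents give LLOQs only for CSF and tissue and no human plasma half-life:** the half-life, and R = Cmax at 2 mg divided by plasma LLOQ, varied from 2 to 1000.

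**Worked case: 6 h half-life, absorption rate 1 per h, samples to 24 h.** C(t) = exp(−0.1155t) − exp(−t), in units for 2 mg, with a maximum of 0.667.

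| h | 0.5 | 1 | 2 | 4 | 12 | 24 |
|---|---|---|---|---|---|---|
| C | 0.337 | 0.523 | 0.658 | 0.612 | 0.250 | 0.0625 |

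Areas by linear-up/log-down trapezoid:

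- 0 to 4 h: 0.084 + 0.215 + 0.591 + 1.270 = 2.16.
- 4 to 12 h: 8 × (0.612 − 0.250) / ln(0.612/0.250) = 3.23.
- 12 to 24 h: 12 × (0.250 − 0.0625) / ln 4 = 1.62.
- Cumulative: 2.16 to 4 h, 5.39 to 12 h, 7.02 to 24 h (rounded).

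Results:

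- R = 10: LLOQ = 0.0667. At 2 mg the 24 h value (0.0625) is below it, so t = 12 h; from 4 mg upward t = 24 h. Ratio = 7.02/5.39 = 1.30.
- R = 2: LLOQ = 0.334. At 2 mg the 12 h value (0.250) is below it, so t = 4 h; at 32 mg the 24 h value is 16 × 0.0625 = 1.0, so t = 24 h. Ratio = 7.02/2.16 = 3.25.
- R = 20: LLOQ = 0.033. All doses reach 24 h. Ratio = 1.00.

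**Other cases, 32/2 mg ratio, linear-up/log-down:**

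| Assumed kinetics | Ratio |
|---|---|
| 3 h half-life | 1.89 at R = 2 to 5; 1.09 at 10 to 100; 1.00 at 1000 |
| 12 h half-life | 1.61 at R = 2; 1.00 from R = 5 |
| 4 h plus a slow phase (200 to 400 h, 1 to 2%), Day 14 and 28 included | 2.26 to 2.49 at R = 10; 2.08 to 2.20 at 20 to 50; 1.12 to 1.15 at 100; 1.00 at 1000 |

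In the last row the ratio of about 2 arises where Day 14 is quantifiable at the higher doses but not at 2 mg. It would shift with a different split between the phases. With the linear trapezoid the largest ratio over all cases is 3.87, and the apparent log-log dose slope reaches 1.43 against a true 1.00.

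**AUC0-24 in the same cases (linear trapezoid, values below LLOQ set to 0).** In the worked case the full linear area is 2.16 + 3.45 + 1.875 = 7.48.

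- R = 10: the 2 mg area is 2.16 + 3.45 + 12 × 0.250/2 = 7.11. Ratio = 7.48/7.11 = 1.05.
- R = 2: the 2 mg area is 2.16 + 8 × 0.612/2 = 4.61. Ratio = 7.48/4.61 = 1.62.
- All cases: 1.00 to 1.05 for R ≥ 10, 1.00 to 1.20 at R = 5, and 1.16 to 1.62 at R = 2.

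**Sentinels.** At the same dose, stopping at 48 h instead of 24 h gives 1.00 to 1.07 for half-lives up to 6 h, 1.00 to 1.27 at 12 h and 1.54 at 24 h. One of 9 active patients is affected, so even 1.54 moves a cohort mean by only 0.54/9 = 6%.

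**The case against.** The strongest reply is that nothing has been shown to be distorted. Plasma LLOQ and half-life are unknown, and the ratio is exactly 1.00 whenever every dose is quantifiable to the same last sample. That stands: the effect is possible and unbounded, not demonstrated.

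Section 10.4 also lists and plots individual profiles, so unequal end times would be visible. The analyses are mainly descriptive, no proportionality test is planned, and escalation rests on safety data. These points limit the consequence, but a descriptive table of area by dose can still mislead. The clause on additional parameters names none and leaves the choice until after the data are seen. Section 10.1 defers details to an SAP whose text is not in the material available, so the missing rules may be there; if so, the remedy belongs there too.

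Four stronger readings are tempting but not supported:

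- A reader might infer that no usable single-dose exposure measure is planned. Cmax is in the same table and is unaffected by t.
- A reader might infer that the sentinels' 48 h sample itself produces a dose trend. There is one active sentinel in every cohort, so it mainly adds spread within cohorts.
- Table 3 schedules treatment-naive patients so that "all patients will have blood samples collected for PK analysis predose and 30 minutes" and up to 4 h after their first dose. A reader might infer that these short profiles enter the Table 8 comparison. Nothing in the protocol pools them.
- At 32 mg "all patients will have urine samples for PK analysis collected at 0 to 4 hours, 4 to 8 hours" and 8 to 24 h. A reader might infer that renal clearance needs a matching plasma area. Renal clearance is not a listed parameter.

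**Conclusion.** The concern holds as a possibility that the plan leaves open. AUC0-t is the only planned single-dose AUC, its end time depends on LLOQ and so on dose, and it is to be compared over a 16-fold dose range. Where end times differ in the cases run, the bias makes exposure look more than proportional. Its size ranges from none to more than 3-fold between 32 and 2 mg, and is about 2-fold where Day 14 is quantifiable only at the higher doses. All these sizes rest on assumed half-lives, an assumed slow phase and an assumed Cmax-to-LLOQ ratio. The statement that the planned comparison will be distorted goes further than the documents allow.

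**What to change.** Add AUC0-24 to Table 8, computed from the 0 to 24 h samples scheduled for every single-dose patient. State in Section 10.4 or the SAP that the cross-dose comparison uses AUC0-24 and Cmax. In the same place:

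- State the rule for values below LLOQ and the trapezoid method. Report the plasma LLOQ, and note that AUC0-24 is still biased if the 2 mg curve lies close to it.
- Keep AUC0-t as a descriptive value, with its end time shown for each patient.
- Report the 48 h, Day 14 and Day 28 values as concentrations, outside the area used for comparison.
- If first-dose profiles of treatment-naive patients are ever pooled with single-dose profiles, compare them over 0 to 4 h only.

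The cost is wording in Table 8 and the analysis plan. It needs no extra blood draws or visits. The rules should be fixed before the concentrations are unblinded.
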